2.0 Specific Aims and Hypothesis

The **first primary aim** is to define the impact of HF (20 Hz) rTMS targeting the LDLPFC and LSPC on ACC activation in individuals with schizophrenia during in-scanner CC task performance. We predict that HF rTMS targeting the LDLPFC and LSPC will result in increased functional activation in the ACC during performance of an in-scanner CC task. The **second primary aim** of this study is to define the impact of HF rTMS targeting the LDLPFC and LSPC on CCN functional connectivity (FC). We hypothesize that HF rTMS of the LDLPFC and LSPC will result in increased FC between the LDLPFC, LSPC, and ACC during performance of an in-scanner CC task. An **exploratory aim** of this study is to determine the effects of HF rTMS targeting the LDLPFC and LSPC will examine if HF rTMS targeting the LDLPFC and LSPC is associated with improved performance during on in-scanner CC task.

Primary Aim 2 Prediction

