3.0 Study Design

This will be a single site pilot study. 20 subjects with EPP, defined as medical record documentation of the onset of clinically significant psychotic symptoms within the past 10 years, will be enrolled. Prior to randomization subjects will undergo fMRI during CC task (Stroop Color-Word paradigm) and resting-state paradigms. This baseline scan will also

include a high-resolution structural sequence for neuronavigation purposes. Then, on two separate days, each occurring one-week apart, subjects will receive one session of excitatory (20 Hz) rTMS targeting the LDLPFC and one session targeting the LSPC. The order of stimulation sites will be randomized and counter-balanced. Immediately following each session, subjects will undergo repeat fMRI during CC and RS paradigms. We will also examine the effect of rTMS on CC performance.

rTMS Set up and Administration

rTMS will be delivered using the Magventure MagPro X100 Magnetic Stimulator (Magventure Inc., Alpharetta, Georgia). Motor threshold (MT) will be determined using single pulse stimulation over the left primary motor cortex, assessed as the lowest intensity producing five visible movements of the right abductor pollicis brevis out of ten stimulations.

High Frequency rTMS

High frequency rTMS, or rTMS greater than 5 Hz, leads to faciliatory effects on brain excitability^{20-24,31}. Previous studies have demonstrated that administration of as little as a single train or a small number of trains are able to produce an immediate increase in cortical excitability²⁴. Additionally, earlier investigations have utilized high frequency rTMS in schizophrenia populations, demonstrating that the treatment is safe, well-tolerated and capable of altering cognitive performance^{30,32}. Our group has employed 20 Hz rTMS at 110% of motor threshold in a stimulation protocol in-line with the current proposal to improve cognitive function in an EPP cohort³⁰. High Frequency rTMS Protocol: Subjects will receive two sessions of HF rTMS, targeting the LDLPFC and LSPC, within the following stimulation parameters: 20 Hz, at 120% of MT, 60 trains (1.0 second per train), 20 pulses per train, inter-train interval of 20 seconds, for a total of 1200 pulses over 21 minutes. This stimulation protocol is within safety limits for rTMS^{21,33,34}.

Neuronavigation

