13.0 Statistical Considerations

Analyses

Power Analyses

In terms of the power to detect a significant effect of HF rTMS on CC neurocircuitry or performance, there are no known calculations with EPP patients. However, previous investigations, including our own, used similar stimulation designs when investigating the effects of rTMS on overall cognitive performance. These studies demonstrated statistically significant results with sample sizes consistent with the current proposal³², and Cohen's effect sizes of d = 0.92 and 1.15, respectively^{30,32}. Though these previous studies examined different cognitive constructs than the CC task in this current protocol, these studies do provide evidence that a similar stimulation design is sufficient to elicit a biologic response and assumedly appropriate for investigating the effects of rTMS on CC.

We believe that for the purpose of this pilot study, we can demonstrate significant results with a sample size of 16 (eight per group). This accounts for the effect size estimate derived from the literature, d = 1.1, and the estimation of power to detect an effect at .75, utilizing a one-sided independent test and significance levels of 0.05.

Statistical Analyses

Preliminary analyses will consist of descriptive statistics for all outcome variables, including summary statistics, graphical displays of distributions, and spaghetti plots of individual data over time to detect possible data errors. Demographic and clinical characteristics at baseline will be examined using parametric or nonparametric test statistics as appropriate. Any demographic variables that show significant differences will be added to the final models as covariates in order to ensure that the observed stimulation effects are not spurious or due to demographic confounds.

To minimize the potential for Type II error, all treatment comparisons will be evaluated based on a one-sided significance level of 0.05. To compare overall effect of stimulation over time for the two groups, a set of multivariate repeat measures analysis of variance (ANOVA) will be utilized, with stimulation as the between-group factor and time as the within-subject factor.

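### Section 13.0 analyses and powers stimulation as a between-group factor although every subject receives both sites, and neither stated power follows from its own inputs

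*Combined protocol and SAP*

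**What the plan says.** **Design.** In Section 3.0, after a baseline scan, "subjects will receive one session of excitatory (20 Hz) rTMS targeting the LDLPFC and one session targeting the LSPC", one week apart, each followed by a repeat scan. Site order is randomised and counter-balanced. The Study Procedures Table (Attachment 1) agrees: baseline MRI at Visit 1, stimulation and post-stimulation MRI at Visits 2 and 3, and randomisation to order only. There is no sham condition.

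**Aims.** Section 2.0 gives a direction for change after stimulation: "We predict that HF rTMS targeting the LDLPFC and LSPC will result in increased functional activation in the ACC" and "We hypothesize that HF rTMS of the LDLPFC and LSPC will result in increased FC between the LDLPFC, LSPC, and ACC". The exploratory aim asks whether stimulation "is associated with improved performance during on in-scanner CC task". The visible text does not rank one site above the other.

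**Analysis.** Section 13.0 reads: "To compare overall effect of stimulation over time for the two groups, a set of multivariate repeat measures analysis of variance", "with stimulation as the between-group factor and time as the within-subject factor". It also says: "To minimize the potential for Type II error, all treatment comparisons will be evaluated based on a one-sided significance level of 0.05".

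**Power.** There are two statements. Section 3.0 (Sample Size) claims 0.8 for all planned analyses with 16 subjects, effect size 0.6, alpha 0.05 with no sidedness given, and within-subject correlation 0.5. Section 13.0 takes 16 subjects as eight per group with d = 1.1, and refers to "the estimation of power to detect an effect at .75, utilizing a one-sided independent test and significance levels of 0.05".

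**The concern.** The analysis section describes a parallel-group trial, whereas the design section describes a crossover with a common baseline. An analyst following Section 13.0 literally has no between-group stimulation factor to enter, because each subject belongs to both stimulation conditions. Some other model would have to be chosen, and the plan does not say which.

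The two power statements inherit the split. One assumes paired data and the other independent groups, with different effect sizes and different target power. If neither holds under its own inputs, the reader cannot tell what 16 completers can detect, or for which contrast. The study is meant to supply target-engagement data for later trials, so a null result would be hard to interpret.

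The one-sided rule depends on the same choice. It needs a contrast with a stated direction, and the model as named does not identify one.

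**Working it through.** **1. Design against model**

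| Item | Sections 2.0 and 3.0, Attachment 1 | Section 13.0 |
|---|---|---|
| Stimulation | both sites in every subject | between-group factor |
| What is randomised | order of sites | not stated; two groups, eight each |
| Comparison in the aims | increase after stimulation | group comparison over time |
| Power basis | paired, correlation 0.5 | independent test |

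The only groups of eight that the design creates are the two orders. They differ by site at Visit 2 and swap at Visit 3.

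To size the mismatch, let the outcome SD be σ and all correlations 0.5. A site difference taken between two groups of eight has variance 2σ²/8 = 0.25σ², before any covariate adjustment. The within-subject difference in 16 subjects has variance 2σ²(1 − 0.5)/16 = 0.0625σ². The between-group version is four times as variable.

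**2. Section 3.0 power (stated 0.8)**

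Inputs: n = 16, effect 0.6 in SD units, correlation 0.5, alpha 0.05.

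- Standardised paired effect: 0.6/√(2(1 − 0.5)) = 0.6.
- Noncentrality: 0.6 × √16 = 2.4, with 15 df.
- One-sided cut-off 1.753: power **0.740**. Two-sided cut-off 2.131: power **0.612**.
- Normal approximation: 0.775 and 0.670.

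None of these is 0.8. At correlation 0.5, 0.8 needs 19 completers one-sided (0.808) or 24 two-sided (0.804). The result is sensitive to the correlation: 0.614 one-sided and 0.475 two-sided at 0.3; 0.905 and 0.825 at 0.7. The plan states 0.5.

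**3. Section 13.0 power (stated 0.75)**

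Inputs: 8 per group, d = 1.1, one-sided 0.05, independent test.

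- Noncentrality: 1.1 × √(8/2) = 2.2, with 14 df.
- One-sided: power **0.673** (normal approximation 0.711). Two-sided: 0.535.
- Nine per group gives 0.722 and ten gives 0.764, so 0.75 one-sided needs ten per group by the t calculation.

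**4. A contrast that 16 completers can support**

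Take the mean of the two post-stimulation scans minus baseline, assuming 0.6 applies to both sites and all three scans correlate at 0.5.

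- Variance of the mean of two scans: σ²(1 + 0.5)/2 = 0.75σ². Its covariance with baseline is 0.5σ².
- Variance of the contrast: 0.75 + 1 − 2(0.5) = 0.75σ².
- Standardised effect: 0.6/√0.75 = 0.693. Noncentrality: 0.693 × 4 = 2.77.
- Power: **0.841** one-sided, 0.736 two-sided.

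**5. Where one-sided 0.05 can apply**

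A 1-df F is a squared t, so one-sided 0.05 is F at the 0.10 level plus the predicted sign (for 1 and 14 df: 3.10, against 4.60 for F at 0.05). An F with more than one numerator df has no one-sided form. With three scans and two groups of eight, the multivariate time or interaction test is F(2,13), with its usual 0.05 cut-off at 3.81.

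**The case against.** **Groups do exist.** The two orders are randomised groups, and eight per group fits them. An ANOVA with order between subjects and visit within subject is a legitimate crossover analysis: change from baseline sits in the visit effect, and site in the order-by-visit interaction. This stands as far as it goes, so it would be wrong to say the design has no groups. But the factor named is stimulation, not order, and the independent-test power describes neither of those terms.

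**The power figures may refer to something else.** The averaged contrast in step 4 exceeds 0.8 one-sided, and ten per group (the 20 enrolled) exceeds 0.75. The plan names neither: Section 3.0 claims 0.8 for all planned analyses with 16 subjects, and Section 13.0 says eight per group.

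**The hypotheses are directional, so one-sided testing is legitimate.** Agreed for site-minus-baseline contrasts. Each holds its 0.05 level as a test of mean change.

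**A stronger reading is tempting.** A reader might infer that the blanket one-sided rule doubles the error rate to 0.10. That happens only if the tail is chosen after seeing the data or an F-test p value is halved (for F(2,13), a cut-off of 2.76 instead of 3.81). The documents plan neither, and no stated aim depends on comparing LDLPFC with LSPC. The plan does not name that comparison; it is inferred because no other two stimulation conditions exist. The figure captioned as the Aim 2 prediction is also not visible, so the absence of a direction between sites can be asserted only for the visible text.

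**Conclusion.** The point holds as a mismatch between design and analysis, together with two power figures that their own inputs do not support. The shortfall is 0.74 (one-sided) or 0.61 (two-sided) against 0.8 for a single paired contrast, and 0.67 against 0.75 for the independent test. These are t-based calculations with the plan's own sample size, effect size and correlation; the normal approximation does not reach the stated values either.

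The sidedness issue is a minor clarification within this point. It is not evidence of an inflated error rate: the level stays at 0.05 if the direction is fixed in advance and F tests are read in the usual way.

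Overall the point is minor. The data that the design collects can support the right analysis; what needs correcting is the written model and the claimed power.

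**What to change.** **Section 13.0, model.** Replace the two groups and the between-group stimulation factor with a within-subject model over three conditions (baseline, post-LDLPFC, post-LSPC). Name the site-minus-baseline contrasts, or their average, that carry the direction in Section 2.0.

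**Sections 3.0 and 13.0, power.** Give one statement for the named contrast and its sidedness. Options at the plan's inputs:

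- One site against baseline, 16 completers: 0.74 one-sided.
- Mean of both post-stimulation scans against baseline, 16 completers: 0.84 one-sided, if 0.6 applies to both sites and all scans correlate at 0.5.
- 0.8 one-sided for one site against baseline: 19 completers, or 24 enrolled at 20% drop-out (19/0.8 = 23.75).

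**Section 13.0, sidedness.** Keep one-sided 0.05 for the named directional 1-df contrasts. Test any LDLPFC against LSPC comparison two-sided at 0.05, or state that none is intended. Read F terms with more than one df at the usual upper-tail 0.05.

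**Cost.** This is a wording change with no new data unless the sponsor chooses to enrol more. The stated power becomes less favourable. Any non-directional comparison loses power against a one-sided reading: 0.74 to 0.61 at an assumed paired effect of 0.6, and 0.31 to 0.20 at an assumed 0.3, which may be nearer the mark for a difference between two active sites. The directional contrasts lose nothing.

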
Visit Number	1 ^c	2	3	4 ^d
Day ^b		0	7	21
Informed Consent	Х			
Screening (Demographics, Inc/Exc,	Х			
Medical & Psychiatric History of Self and				
Family)				
SCIDª	Х			
Physical Exam	Х			
CGI-S	Х			
CGI-I		Х	Х	
Vitals	Х	Х	Х	
Urine Drug Screen	Х			
Pregnancy Test	Х	Х	Х	
Motor Threshold Determination	Х			
MRI – Baseline	Х			
Randomization (Order of Study		Х		
Intervention)				
Neuro Navigation		Х	Х	
rTMS Administration (LDLPFC or LSPC)		Х	Х	
Post Stimulation MRI-CC Task		Х	Х	
PANSS	Х			
AIMS	Х	Х	Х	
C-SSRS	Х	Х	Х	
Adverse Events	Х	Х	Х	Х
Concomitant Medication	Х	Х	Х	Х
^a If subject received a SCID interview within 6 months of screening, it may not be				
repeated at the discretion of the PI				
^p Ideal time frame for administration will be on the same day of two consecutive				
discretion of the PL and will not be a protocol violation				
^c Visit window for Visit 1 is 0-30 days				
^d Visit 4 may occur by phone and ideally will occur 14 days after Visit 3. Visit				
window deviations will be granted at the discretion of the PI and will not be a				
protocol violation.				

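### Section 13.0 makes stimulation a between-group factor although every subject receives both sites, and it designates no post-versus-baseline test for Aims 1 and 2

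*Combined protocol and SAP*

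**What the plan says.** Section 3.0 describes a within-subject design: on two days a week apart, "subjects will receive one session of excitatory (20 Hz) rTMS targeting the LDLPFC and one session targeting the LSPC". It adds: "The order of stimulation sites will be randomized and counter-balanced". One task scan precedes randomisation and one follows each session. The Study Procedures Table (Attachment 1) agrees; its randomisation row begins "Randomization (Order of Study" and ends with the word Intervention. The Sample Size text in Section 3.0 powers a counter-balanced design with 16 completers, effect size 0.6, within-subject correlation 0.5 and power 0.8 for every planned analysis.

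Section 13.0 describes something else. Its power text says "we can demonstrate significant results with a sample size of 16 (eight per group", with d = 1.1 and power .75, "utilizing a one-sided independent test and significance levels of 0.05". Its analysis text begins "To compare overall effect of stimulation over time for the two groups" and specifies a multivariate repeated-measures ANOVA "with stimulation as the between-group factor and time as the within-subject factor". It also says that "all treatment comparisons will be evaluated based on a one-sided significance level of 0.05".

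Section 2.0 states both primary hypotheses as increases: in ACC activation (Aim 1), and in connectivity among the LDLPFC, LSPC and ACC (Aim 2).

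**The concern.** Across the two sessions, site is crossed within subject, so it cannot be a between-group factor. The only between-subject factor the full design creates is the order of the sites. Section 13.0 does not say what its two groups are, which scans are the levels of time, or which term tests Aim 1 or Aim 2.

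This matters because both aims predict a rise, and a rise at both sites is compatible with them. A term that compares one site with the other, or one order with the other, cancels a common rise. Only a comparison with baseline detects it. The study is meant to supply target-engagement data for later trials, so the test that decides engagement should be fixed before the data are seen.

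**Working it through.** **Inputs.** From Section 3.0: 16 completers, effect 0.6, correlation ρ = 0.5. From Section 13.0: 8 per group, d = 1.1, one-sided 0.05. Assumed: effect in units of the single-scan SD, compound symmetry, and 8 subjects per order.

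**1. The plan's own power figures.**
- Section 13.0, two independent groups: noncentrality 1.1 × √(8/2) = 2.2. One-sided power is 0.67 (t, 14 df) or 0.71 (normal), against the stated .75.
- Section 3.0, one post scan against baseline: standardised difference 0.6/√(2(1 − 0.5)) = 0.6, noncentrality 0.6 × √16 = 2.4. One-sided power is 0.74 (t, 15 df) or 0.775 (normal), against the stated 0.8.

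Neither figure reproduces on its plain reading, and the two rest on different designs.

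**2. Terms involving the group factor.** Take the groups as the two orders, with all three scans as levels of time and +0.6 SD at both sites:

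| Order | Baseline | First post scan | Second post scan | Mean |
|---|---|---|---|---|
| LDLPFC first | 0 | 0.6 | 0.6 | 0.4 |
| LSPC first | 0 | 0.6 | 0.6 | 0.4 |

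The rows are identical. The group effect is 0.4 − 0.4 = 0 and the group-by-time effect is zero at every scan. Both terms reject only at the nominal rate: 0.051 and 0.050 in 40,000 simulated trials.

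**3. Omnibus time term, same layout.** The means 0, 0.6, 0.6 deviate from 0.4 by −0.4, 0.2, 0.2; the squares sum to 0.16 + 0.04 + 0.04 = 0.24. Noncentrality = 16 × 0.24/(1 − 0.5) = 7.68. Power is 59% for the multivariate test (2 and 13 df) and 65% for the univariate test (2 and 28 df). Both tests are non-directional.

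**4. Named post-minus-baseline contrasts.**
- Mean of the two post scans minus baseline: variance 1.5(1 − ρ) = 0.75, standardised effect 0.6/√0.75 = 0.693, noncentrality 0.693 × 4 = 2.77. Power (15 df) is 84% one-sided and 74% two-sided. Adjusted for order (14 df), one-sided power is still 84% (0.839).
- Each site minus baseline: 74% one-sided, as in step 1.

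**5. Sensitivity of the pooled contrast (one-sided).**
- Correlation 0.3: SD √(1.5 × 0.7) = 1.025, power 72%.
- Correlation 0.7: SD √(1.5 × 0.3) = 0.671, power 96%.
- Only one site active: mean rise 0.3, standardised effect 0.3/√0.75 = 0.346, power 37%. The active site against baseline keeps 74%.
- Level 0.025 in place of 0.05: 74%. Each site minus baseline at 0.025: 61%.

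**The case against.** The best defence is that the plan has a natural reading. The design offers one between-subject factor, order. 'Eight per group' fits 16 counter-balanced completers, and Section 3.0 schedules exactly three scans. On that reading time includes baseline, and its test detects a common rise with 59% to 65% power. The one-sided rule in Section 13.0 also points towards a directional 1-df contrast, which is available within the same model at 84%.

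Much of this stands, and it rules out three stronger inferences.

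- A reader might infer that the planned ANOVA cannot detect a rise. It can, through the time factor, if baseline is a level.
- A reader might infer that power for the aims could be as low as 5%. That figure belongs to terms that do not test a common rise, or to a version of time that leaves out the baseline scan.
- A reader might infer that a within-subject analysis simply delivers the promised 0.8. The 84% is one-sided, pooled over sites, and assumes that both sites are equally active. Tested two-sided it is 74%. Setting 84% beside 59% to 65% also compares a one-sided 1-df test with non-directional 2-df tests.

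What the defence does not supply is the text. Section 13.0 still labels the between-group factor stimulation, and the power statement still assumes an independent test. No section designates the time term, or any contrast, as the test of either aim. A three-level omnibus time test is also not the one-sided test that Section 13.0 requires. Pilot status does not settle this, because the plan makes formal significance tests and power claims.

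**Conclusion.** The point holds on the text and needs no figure: Section 13.0 conflicts with Section 3.0 and the Study Procedures Table on what is compared between subjects, and it leaves both primary aims without a designated test. It should be corrected before analysis.

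The size is the difference between terms that reject at about 5%, an omnibus time test at 59% or 65%, and a named directional contrast at 84% (pooled) or 74% (per site). The gain over the omnibus test comes from naming a directional 1-df contrast, not from a model that is otherwise unable to deliver one. Of the tests considered at correlation 0.5, only the pooled one-sided contrast meets the 0.8 claimed in Section 3.0. The effect and correlation come from the plan; compound symmetry and equal activity at both sites are assumptions.

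**What to change.** 1. Replace the ANOVA sentence with:

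   > Stimulation site is a within-subject factor; the between-subject factor is order. For each aim the primary test is the within-subject post-stimulation-minus-baseline contrast, one-sided 0.05, by a one-sample t test or the equivalent contrast adjusted for order. LDLPFC minus LSPC is a secondary, order-balanced within-subject comparison, two-sided.

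2. State in advance whether the primary contrast is the mean of the two post scans or each site separately, which connectivity measure or summary serves Aim 2, and whether the primary tests share the 0.05. If they do share it, the one-sided level in item 1 changes accordingly.
3. Bring the neighbouring sentences into line. Limit the one-sided rule to the post-minus-baseline contrasts. Restrict or drop the rule that adds demographic covariates, since no treatment groups are compared.
4. Remove the eight-per-group and independent-test wording. Restate the power in Sections 3.0 and 13.0 for the chosen contrast (for example 84% pooled or 74% per site, one-sided), with its assumptions.
5. Add that there is no sham or unstimulated repeat scan, so results are described as change after stimulation.

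**Cost.** Only wording changes; subjects, scans and data stay the same. The pooled contrast falls to 37% power if one site is inactive. Per-site testing misses the stated 0.8 and adds primary tests. Item 5 discloses the missing control but does not remove the limitation.
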